**Table 2: Guidelines for Interruption and Restarting Study Drug (Continued)**

ADVERSE EVENT	ACTION TAKEN

 
• Skin toxicity (eg, rash, pruritus, etc, unless otherwise specified) (Grade 2-3)
 
	
Step 1: Interrupt INCB050465 until the toxicity has resolved to <math>\leq</math> Grade 1.
 
Step 2: Restart INCB050465 at same dose. If assessed as related to INCB050465, restart at next lower dose.

 
• Exfoliative dermatitis (Grade 1)
 
	
Step 1: Interrupt INCB050465 until the toxicity has resolved.
 
Step 2: Restart INCB050465 at next lower dose. Monitor as clinically indicated.

 
• Exfoliative dermatitis (<math>\geq</math> Grade 2)
 
	Permanently discontinue INCB050465.

 
• Intestinal perforation (any grade)
 
	Permanently discontinue INCB050465.

 
• Pneumocystis jiroveci pneumonia infection
 
	Interrupt INCB050465. Permanently discontinue INCB050465 if Pneumocystis jiroveci pneumonia infection is confirmed.

 
• CMV infection
 
	Subjects with CMV viremia without associated clinical signs of CMV infection should be carefully monitored. Consider interrupting INCB050465 for subjects with CMV viremia and clinical signs of infection until the infection has resolved. Restart INCB050465 reduced by 1 dose level if approved by the medical monitor.

 
• Varicella zoster infection
 
	Interrupt INCB050465. Restart INCB050465 only by approval of the medical monitor.

 
• Any Grade 1 or Grade 2 toxicity unless otherwise specified.
 
	Continue study treatment and treat the toxicity; monitor as clinically indicated.

 
• Any Grade 3 toxicity, if clinically significant and not manageable by supportive care unless otherwise specified.
 
	
Step 1: Interrupt INCB050465 up to 14 days until the toxicity has resolved to <math>\leq</math> Grade 1.
 
Step 2: Restart INCB050465 at same dose. If assessed as related to INCB050465, restart at next lower dose. If interrupted for <math>></math> 14 days, contact the medical monitor for approval to restart INCB050465. Monitor as clinically indicated.


 
• Any recurrent Grade 3 toxicity after 2 dose reductions.
 
	Discontinue study drug administration and follow-up per Protocol. Exceptions require approval of sponsor.

 
• Any other Grade 4 toxicity.
 
	Discontinue study drug administration and follow-up per Protocol. Exceptions require approval of sponsor.

CMV = cytomegalovirus; IV = intravenous; PCR = polymerase chain reaction.

**Table 3: Dose Levels for INCB050465**

Timepoint	Dose
Starting dose	20 mg once daily for 8 weeks
Week 9, Day 1	20 mg once weekly
First dose reduction	10 mg once weekly
Second dose reduction	5 mg once weekly

Note that the first dose reduction is applicable for subject receiving either 20 mg QD or 20 mg once weekly.

#### **5.4.2. Supportive Care Guidelines for Diarrhea/Colitis**

Subjects should be informed to immediately report to the investigator any event of diarrhea. Subjects should receive appropriate supportive care measures as deemed necessary by the investigator. For any Grade  $\geq 1$  diarrhea, subjects should be advised to drink liberal quantities of clear fluids. If sufficient oral fluid intake is not feasible, fluid and electrolytes should be substituted via IV infusion. Subjects should try to eat: 5 to 6 small meals per day; low-fat, high-protein foods; and cooked instead of raw vegetables. Subjects may supplement their diet with bananas, rice, applesauce, and toast to reduce the number of bowel movements, and may also try crackers, gelatin, noodles, or oatmeal. Subjects should avoid fried, fatty, greasy, or spicy foods; milk, milk products, and acidic drinks; high-fiber foods and foods that cause gas; and alcohol, caffeine, and herbal supplements (Coutre et al 2015).

For each occurrence, attempts should be made to rule out other causes, such as metastatic disease or bacterial or viral infection (including CMV), which might require additional supportive care.

It may be necessary to perform conditional procedures such as colonoscopy with biopsy as part of evaluation of the event. Note that several courses of steroid tapering may be necessary as symptoms may worsen when the steroid dose is decreased.

Subjects should be carefully monitored for signs and symptoms of enterocolitis (such as diarrhea, abdominal pain or cramping, blood or mucus in stool, with or without fever) and of bowel perforation (such as peritoneal signs and ileus).

#### **5.4.3. Definition for Immune-Related Adverse Events**

Adverse events of a potential immunologic etiology, or immune-related AEs (irAEs), may be defined as an AE consistent with an immune phenomenon associated with study drug exposure after all other etiologies have been eliminated. Immune-related AEs may be expected based on previous experience with INCB050465 and other drugs (eg, idelalisib) that inhibit PI3K $\delta$ . Special attention should be paid to AEs that may be suggestive of potential irAEs. Based on emerging data from the ongoing Study INCB 50465-101, most irAEs occur after the first 9 weeks of study drug administration. However, an irAE could occur at any time. Suspected irAEs should be discussed with the medical monitor when possible.

Subjects should receive appropriate supportive care measures as deemed necessary by the treating investigator. Suggested supportive care measures for the management of drug-related AEs with potential immunologic etiology are outlined in Table 2 and Section 5.4.2. For each AE, attempts should be made to rule out other causes, including but not limited to metastatic disease or bacterial or viral infection, which might require specific supportive care.

#### **5.5. Study Treatment Discontinuation**

The decision to discontinue study treatment will not constitute study completion. In the event that study treatment is discontinued, the treatment phase will be considered complete, and the follow-up phases will begin.

### 5.5.1. Criteria for Study Treatment Discontinuation

Subjects **must** permanently discontinue study treatment for any 1 the following:

- The subject has experienced an unacceptable toxicity defined as follows:
  - Occurrence of an AE that is related to treatment with the study drug that, in the judgment of the investigator or the sponsor's medical monitor, compromises the subject's ability to continue study-specific procedures or is considered to not be in the subject's best interest.
  - Persistent AE requiring a delay of therapy for more than 2 weeks (14 days) unless a greater delay has been approved by the sponsor.
- The subject is unable to tolerate INCB050465.
- The subject has an objective radiographic tumor response of PD/PMD.
- Further participation would be injurious to the subject's health or well-being, in the investigator's medical judgment.
- The subject becomes pregnant.
- Informed consent is withdrawn. Note: Informed consent withdrawn means that the subject can no longer receive study treatment **and** can no longer be followed.
- The study is terminated by the sponsor.
- The study is terminated by the local health authority, IRB, or IEC.

A subject **may** be discontinued from study treatment in the following situations:

- If a subject is found not to have met eligibility criteria, then the medical monitor and investigator will collaborate to determine whether the subject should be withdrawn from the study. (Note: Not applicable in Canada.)
- If a subject is noncompliant with study procedures or study drug administration in the investigator's opinion, then the sponsor should be consulted for instruction on handling the subject.

### 5.5.2. Procedures for Study Treatment Discontinuation

**If a subject discontinues study treatment, then the following should occur:**

- The reason(s) for discontinuation must be documented in the subject's medical record and in the eCRF.
- The end-of-treatment (EOT) visit should be performed.
- If the EOT visit coincides with a regular study visit, then the EOT evaluations will supersede those of that scheduled visit, and the data will be entered in the EOT visit in the eCRF.
- The date of the EOT visit should be recorded in the IWRS.
- Subjects must be followed for safety for no less than 30 days after the EOT visit or until study drug-related toxicities resolve, return to baseline, or are deemed irreversible, whichever is longest.

If a subject actively withdraws from study treatment, then the subject will continue in the safety and survival follow-up periods of the study. The study monitor or sponsor must be notified if a subject actively withdraws from study treatment or withdraws the informed consent. If a subject withdraws informed consent, then the subject will have completed the study, and no additional data collection should occur.

## **5.6. Concomitant Medications**

All concomitant medications and treatments must be recorded in the eCRF. Any prior medication received up to 30 days before the date of study drug administration (Day 1) will be recorded in the eCRF. Concomitant treatments and/or procedures that are required to manage a subject's medical condition during the study will also be recorded in the eCRF.

### **5.6.1. *Pneumocystis Jirovecii* Prophylaxis**

All subjects are required to receive a standard PJP prophylaxis regimen determined by the investigator. Examples of standard PJP prophylaxis therapies for this population include trimethoprim-sulfamethoxazole, atovaquone, dapsone with or without pyrimethamine, and pentamidine (NCCN 2016). Due to reports of cross-sensitivity between sulfonamides and dapsone, all subjects who have a known or suspected allergy to sulfonamides must receive either inhaled pentamidine or atovaquone for PJP prophylaxis. Prophylaxis should be given while subjects are receiving study treatment and should continue for 2 to 6 months after the last dose of study treatment.

### **5.6.2. Supportive Care Measures**

Supportive care should be administered to subjects as per the institutional policy at the site for the standard therapy that the subject will receive. Additional information may be available in the appropriate package inserts. This includes the use of prophylactic growth factors, which should be based on American Society of Clinical Oncology guidelines for the use of white blood cell growth factors (Smith et al 2006) and the investigator's clinical judgment.

### **5.6.3. Restricted Medications**

- Use of systemic corticosteroid doses  $\leq$  10 mg/day prednisone (or equivalent) is permitted but discouraged from the screening visit through the EOT visit.
- Use of weak or moderate inducers or inhibitors of CYP3A4 (Appendix B) is discouraged, and investigators should seek other options where possible.
- P-glycoprotein substrates of clinical relevance should be used with caution (ie, aliskiren, ambrisentan, colchicine, dabigatran etexilate, digoxin, everolimus, fexofenadine, imatinib, lapatinib, maraviroc, nilotinib, posaconazole, ranolazine, saxagliptin, sirolimus, sitagliptin, talinolol, tolvaptan, topotecan).

#### 5.6.4. Prohibited Medications and Therapies

- Use of potent inducers and inhibitors of CYP3A4 are prohibited ([Appendix B](#)). Based on the low overall bioavailability of topical ketoconazole, there are no restrictions on topical ketoconazole.
- Use of any anticancer medications other than the study medication as described (see [Section 3.2](#)) through the 30-day follow-up is prohibited.
- Use of systemic corticosteroid doses > 10 mg/day prednisone (or equivalent) is not permitted from the screening visit through the EOT visit.
- Radiation therapy.

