**Table 2: Guidelines for Interruption and Restarting Study Drug**

ADVERSE EVENT	ACTION TAKEN
Chemistry	

 
• AST and/or ALT is Grade 3 (<math>> 5.0 \times \text{ULN}</math>).
 
 
Note: In subjects with liver metastasis-related elevations at baseline, contact sponsor to discuss clinical management and possible dose reductions.
	
Step 1: Interrupt INCB050465 and monitor weekly until the toxicity has resolved to <math>\leq</math> Grade 1.
 
Step 2: Restart INCB050465 at next lower dose with medical monitor approval. Monitor as clinically indicated.

Hematology	

 
• Grade 3 ANC (<math>< 1.0 \times 10^9/\text{L}</math>).
 
• Platelet count is Grade 2 (50 to <math>< 75 \times 10^9/\text{L}</math>) for subjects who enrolled with platelets <math>> 100 \times 10^9/\text{L}</math>.
 
• Platelet count is Grade 3 (<math>< 50 \times 10^9/\text{L}</math>) for subjects who enrolled with platelets <math>\leq 100 \times 10^9/\text{L}</math>.
 
	
Step 1: Interrupt INCB050465 up to 14 days until the toxicity has resolved to <math>\leq</math> Grade 1 or pretherapy baseline. For Grade 3 ANC, monitor at least weekly.
 
Step 2: Restart INCB050465 at same dose; monitor as clinically indicated.

 
• Grade 4 ANC (<math>< 0.5 \times 10^9/\text{L}</math>).
 
• Grade 3 or Grade 4 ANC with an oral temperature of at least <math>38.5^\circ\text{C}</math> OR with <math>\geq</math> Grade 3 infection.
 
• Platelet count is Grade 4 (<math>< 25 \times 10^9/\text{L}</math>).
 
	
Step 1: Interrupt INCB050465 up to 14 days until the toxicity has resolved <math>\leq</math> Grade 1. (For Grade 4 ANC, monitor ANC at least weekly.)
 
Step 2: Restart INCB050465 at same dose. If assessed as related to INCB050465, restart at next lower dose. Monitor as clinically indicated.

Other toxicities	

 
• Diarrhea/colitis (Grade 1)
 
	
Step 1: Treat with antimotility agents (eg, 4 mg loperamide followed by 2 mg every 4 hours or after every unformed stool) and initiate supportive care (see Section 5.4.2). If not improved after 48 hours, treat per guidance for Grade <math>\geq 2</math>.

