
 
• Diarrhea/colitis (Grade <math>\geq 2</math>)
 
	
Step 1: Interrupt INCB050465. Perform work-up for infection (including CMV, C. difficile, etc). Initiate or continue supportive care (see Section 5.4.2). Consider colonoscopy with biopsy for Grade <math>\geq 3</math>.
 
Step 2: If infection is ruled out, start oral steroids, or consider IV steroids if subject is being given IV fluids. If no improvement with oral steroids, switch to IV steroids.
 
When diarrhea resolves to Grade <math>\leq 1</math>, continue supportive care and taper steroids over 4 weeks. When taper is complete and diarrhea is Grade <math>\leq 1</math>, restart INCB050465 at next lower dose with approval of the medical monitor.
 
If Grade <math>\geq 2</math> diarrhea reoccurs, permanently discontinue INCB050465.

 
• Pneumonitis (Grade 1)
 
	
Step 1: Interrupt INCB050465 until the toxicity has resolved.
 
Step 2: Restart INCB050465 at next lower dose. Monitor as clinically indicated.

 
• Pneumonitis (Grade <math>\geq 2</math>)
 
	
Permanently discontinue INCB050465.

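### Protocol Section 5.6.4 bars systemic steroids above 10 mg/day prednisone equivalent until EOT with no adverse-event exception, while Table 2 directs steroid treatment of diarrhea/colitis followed by a restart of study drug

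*Protocol*

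**What the plan says.** **The restriction.** Section 5.6.4 states that systemic corticosteroids above "10 mg/day prednisone (or equivalent) is not permitted from the screening visit through the EOT visit". No exception follows. Section 5.6.3 adds that doses at or below "10 mg/day prednisone (or equivalent) is permitted but discouraged from the screening visit through the EOT visit".

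**The treatment instruction.** Table 2 (Section 5.4.1) has study drug interrupted and infection investigated for Grade 2 or higher diarrhea/colitis. It then says: "If infection is ruled out, start oral steroids, or consider IV steroids if subject is being given IV fluids". Next comes escalation: "If no improvement with oral steroids, switch to IV steroids". Once diarrhea is back to Grade 1 or lower, the site is to "continue supportive care and taper steroids over 4 weeks", and after the taper to "restart INCB050465 at next lower dose with approval of the medical monitor". Grade 1 events can enter the same pathway: "If not improved after 48 hours, treat per guidance for Grade" 2 or higher. Section 5.4.2 expects repeat courses: "Note that several courses of steroid tapering may be necessary as symptoms may worsen when the steroid dose is decreased".

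**Timing and oversight.** Section 6.3 ties the EOT visit to permanent discontinuation. Section 5.4.1 asks the investigator to contact the sponsor before restarting after a hold of more than 14 days, and Section 5.5.1 requires discontinuation after such a delay unless the sponsor has approved a longer one. After Amendment 4, Section 7.3.1.1 and Table 6 still have sites check that no prohibited medication is in use.

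**The concern.** The two rules apply to the same subjects over the same period. Table 2 tells the site to give steroids, to step up to IV if oral treatment fails, and then to bring the subject back onto study drug. Section 5.6.4 tells the same site that anything above 10 mg/day prednisone equivalent is prohibited until EOT, which such a subject has not reached. Section 5.6.3 discourages even the doses below that limit.

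If the site gives priority to Section 5.6.4, colitis treatment is capped at 10 mg/day at every step, including the IV step after oral failure. This is a safety issue for a toxicity the sponsor expects: colitis and Grade 2 or higher diarrhea are adverse events of special interest in Section 8.4. If the site gives priority to Table 2 and exceeds the cap, it has used a prohibited medication while following the protocol's own management table.

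**Working it through.** This is mainly a comparison of text, with one calculation to indicate frequency. The plan gives no figure of its own to reproduce.

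**Step 1: do the rules overlap in time?**

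| Item | Source | Content |
|---|---|---|
| Window of the ban | 5.6.4 | Screening visit to EOT visit |
| When EOT occurs | 6.3 | At permanent discontinuation of study treatment |
| End of the steroid pathway | Table 2 | Taper complete, then restart at the next lower dose |
| Length of the taper | Table 2 | 4 × 7 = 28 days |

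A subject who restarts has not permanently discontinued and so has not reached EOT. The whole steroid course, including at least 28 days of taper, falls inside the window.

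**Step 2: do they overlap in dose?** Table 2 names no dose, so a course at or below 10 mg/day complies with both rules and any course above it does not. Per kilogram the cap is 10/70 = 0.14 mg/kg/day at an assumed 70 kg (10/50 = 0.20 at 50 kg; 10/100 = 0.10 at 100 kg). Table 2 neither states this cap nor refers to Section 5.6.4.

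**Step 3: does anything reconcile them?** The 28-day taper exceeds the 14-day hold limit, so the sponsor becomes involved under Sections 5.4.1 and 5.5.1, and Table 2 requires medical monitor approval to restart. These provisions govern delay and restart. They limit differences between sites in who restarts, but they neither set a steroid dose nor waive Section 5.6.4.

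**Step 4: how often might it arise?** The only usable rate in the documents is from Study 101 (Section 1.3): serious colitis in 3 and serious diarrhea in 3 of 46 subjects. Whether these were the same subjects is not stated, so both extremes are shown with exact (Clopper-Pearson) 95% limits.

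| | Same subjects | Different subjects |
|---|---|---|
| Rate | 3/46 = 6.5% | 6/46 = 13.0% |
| Exact 95% CI | 1.4% to 17.9% | 4.9% to 26.3% |
| Expected in 100 (Group A) | 6.5 (1.4 to 17.9) | 13.0 (4.9 to 26.3) |
| Expected in 120 (both groups) | 7.8 (1.6 to 21.5) | 15.7 (5.9 to 31.5) |

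At the lowest limit, p = 0.01366, the chance of at least one such subject is 1 − (1 − 0.01366)^100 = 0.747 in 100 subjects and 1 − (1 − 0.01366)^120 = 0.808 in 120.

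These figures count serious colitis or diarrhea, not steroid courses above 10 mg/day. Three things limit the transfer. Study 101 used continuous daily dosing from 5 to 45 mg, with 15 of the 46 subjects at 20 mg. Some events would prove infectious and never reach the steroid step. In the other direction, serious events undercount the Grade 2 or higher events that trigger the pathway.

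**The case against.** The best reply is that no sensible site would withhold colitis treatment that the protocol itself directs. Section 5.4.3 leaves supportive care for immune-related events to the treating investigator and points to Table 2 and Section 5.4.2. Section 8.1.2 calls for all adverse events to be treated appropriately, and Section 5.6 anticipates concomitant treatment needed to manage a subject's condition. On this reading the specific instruction overrides the general list, and what is left is a question of how to code a deviation. This makes undertreatment less likely, but none of these sections waives Section 5.6.4, so a site must infer the override against an unqualified prohibition.

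Several narrower points stand:

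- The conflict depends on dose, because Table 2 gives none.
- Not every course is certain to fall before EOT. Recurrent Grade 2 or higher diarrhea requires permanent discontinuation, so some later courses may follow EOT. Courses that end in a restart cannot.
- The frequency figures are a proxy. The regimen here was changed to reduce adverse events leading to discontinuation, and by Amendment 4 only ongoing subjects would be affected by a change.
- There is no consequence for the efficacy results. Section 5.6 medications are reviewed for the per protocol population, but efficacy is analysed on the full analysis set, and SAP Section 6.3 only lists deviations.

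It can also be argued that an exception for diarrhea/colitis alone is too narrow, because it implies that higher steroid doses stay barred for other immune-related events. They are barred now, however, and diarrhea/colitis is the only toxicity for which Table 2 directs steroids. The narrow exception resolves the stated conflict and leaves other uses exactly as restricted as they are today.

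**Conclusion.** The concern holds. Two rules in the current protocol conflict for any steroid course above 10 mg/day prednisone equivalent that is given under Table 2 and ends in a restart of study drug, and no text says which one governs. The timing follows from Sections 5.6.4 and 6.3 and Table 2 without any assumption.

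The frequency does rest on an assumption: if serious colitis and diarrhea occur at about the Study 101 rate, roughly 6.5 to 13.0 of 100 Group A subjects would have such an event (1.4 to 26.3 over both confidence intervals). How many of these would receive more than 10 mg/day before EOT cannot be derived from the documents.

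The consequence is for subject safety and protocol compliance. No effect on ORR, DOR, PFS or OS is claimed, and no size is put on any change in discontinuations for adverse events. The sponsor should correct it.

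**What to change.** Add an exception to the corticosteroid bullet in Section 5.6.4: *except to treat diarrhea/colitis per Table 2 and Section 5.4.2, with INCB050465 held until the taper is complete.* The hold matches the sequence already in Table 2. Steroid use within the exception is then no longer a prohibited medication. For each such course, record the steroid, the dose, and the start and stop dates.

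The cost is one clause, with no new visits, procedures or subjects. The downside is that some subjects may receive higher steroid doses before EOT than Section 5.6.4 now allows, which is why dose and dates should be kept. Before Amendment 4 concomitant medications were already recorded in full. After it the record is a small added item, because Table 6 asks for concomitant medication data for SAEs only and Section 7.3.1.1 requires eCRF entry only where the medication itself led to study drug discontinuation.

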## 6. STUDY ASSESSMENTS

See the schedule of assessments ([Table 4](#)) and schedule of laboratory assessments ([Table 5](#)) for the timing of all assessments. All assessments mandated throughout the study must be performed on a calendar schedule; delays in treatment administration will not delay performance of assessments. A table of clinical laboratory analytes to be assessed ([Table 8](#)) is provided. The order of assessments is suggested by the order listed within the Schedule of Assessments. See [Sections 6](#) and [7](#) for instructions on each assessment. Further details of study procedures and assessments can be found in the study reference manual.

**Note: Upon implementation of Protocol Amendment 4, only study assessments indicated in [Table 6](#) and [Table 7](#) will be performed.**

